AIM 1: FamCHESS-C Refinement (Months 1–6). Aim 1 is to modify PartnerCHESS in 3 fundamental ways to create FamCHESS-C: 1) Add COVID material already in ACHESS-C, information on vaccines, long-term effects of COVID, and heightened risk from AUD/SUD. 2) Expand PartnerCHESS from focus on romantic partner to any family member. 3) Added content targeting comorbid drug use (psychoeducation, tools to stop, tools for partner to help, and psychoeducation on relationship of drugs to COVID risk and sequelae). Our software design team will recruit 10 dyads for evaluation to assure that we offer appropriate content and delivery in the proper style. The 10 dyads will be recruited from colleagues with lived experience and their personal networks. All refinements will employ rapid cycle testing, refining, and retesting based on feedback from the 10 dyads about difficulties and benefits. Both members of the dyad will engage in think-aloud protocol to assess their in-the-moment reactions as they use the app prototype. Throughout the month of pilot use, dyads will be asked about the extent to which the language, presentation style, and structure are understandable, engaging, intuitive, and relevant to their experience. We will use wireframes, mockups, and html to test prototypes, use feedback to quickly make changes, and test again. We will continue to improve FamCHESS-C throughout the adaptation and pilot phase. Our strategy is based on Shewhart's Plan, Do, Check, Act cycle.²⁹ Refinements to baseline and followup surveys will also be tested with the dyads.

AIM 2: Conduct an RCT to Test Smartphone Control vs. ACHESS-C vs. FamCHESS-C (Months 7-30).

Study design and outcomes. We will conduct a 24-month randomized trial (*N*=198 dyads, 66 in each arm, to yield approximately 180 dyads at 8-month analysis) in which assessment and intervention will all occur remotely. Dyads comprising one person who drinks at risky levels or has AUD (any severity) and one family partner (any family member) will be recruited and randomly assigned to 8 months of either: 1) smartphone control (both drinker and partner receive smartphones with numbers for AA, NA, Al-Anon, ACOA and crisis hot lines); 2) ACHESS-C (drinker receives a phone with ACHESS-C; partner receives a phone with numbers for Al-Anon, ACOA, and crisis hot lines); or 3) FamCHESS-C (drinker and partner receive a phone with FamCHESS-C). In all conditions, both members of the dyad complete baseline assessment plus follow up assessments at 4, 8, and 12 months (i.e. 8-month active app/phone use phase plus follow-up 4 months later).

[figure not shown]
Primary outcomes: 1) drinker % heavy drinking days, 2) dyad quality of life.

Secondary outcomes: 3) dyad relationship satisfaction, 4) dyad psychological/physical conflict, 5) drinker no heavy drinking days, 6) drinker % days alcohol/drug use, 7) dyad COVID vaccination rates, 8) drinker alcohol- and drug-related problems.

Exploratory outcomes: 9) partner % days alcohol/drug use, 10) dyad crisis healthcare use (ER, 30-day hospital readmits), 11) dyad satisfaction with technology.

Rationale for our primary outcomes: Quality of life captures the physical and socioemotional impacts of COVID and alcohol and comorbid drug use for drinkers and partners. Reductions in alcohol and comorbid drug use are the primary means by which we hope to improve quality of life.

Hypothesis 1: Outcomes will be more favorable in FamCHESS-C relative to ACHESS-C, and both will be more favorable relative to smartphone control.

competence, relatedness, and motivation for both drinker and partner, together with interim reductions in the drinker's % days with use of alcohol and drugs, will mediate effects of condition on other improvements in outcomes. For comparisons of ACHESS-C vs. FamCHESS-C, we will also test use of the app as a mediator. Further, we will examine moderation of effects of condition by drinker sex, severity of drinker's baseline alcohol use, drinker engagement in treatment for AUD/SUD, and dyad's baseline relationship satisfaction. Details of measures for all variables in the figure are in the Measures section below.

AIM 4: Conduct a Formative Evaluation Using an Implementation Science Model. Using our Organizational Change Model (OCM),⁷⁵ we will collect qualitative data from 20 drinkers and 20 family partners in the RCT on perceptions of difficulties and benefits of ACHESS-C and FamCHESS-C use. In preparation for this R01 submission we have been conducting an R34 testing the use of a partner-focused CHESS app and feel that the data from that research study, has fulfilled the needs of Aim 4.

Privacy and Confidentiality:

To mitigate the risk of patient breaches of confidentiality, all subjects will be assigned a code number. A list of subject code numbers will be maintained by the UW project director and stored in a password protected spreadsheet. Participant surveys will be identified by code number only. The UW study coordinators will assist patient subjects in choosing codenames and passwords to use to login to the A-CHESS-C or FamCHESS-C system. Patients will be instructed not to use their real names as a codename and will be made aware of the potential dangers of divulging confidential information (e.g. real names or telephone numbers).

Prior to gaining access to our data, all students, faculty and staff must provide our Data Security Officer a copy of their certificates of completion of the UW Madison Human Subjects online training and the online HIPAA Privacy Rule training. Furthermore, they are required to complete training on Center security procedures and policies and sign a Center Data Security Policy Certification upon completion of this training.

Hard copy data, such as surveys, will not contain identifying information. They will be stored in a locked file cabinet in the study coordinators private office. Electronic data, such as A-CHESS-C or FamCHESS-C use data, will be stored on a secure, HIPAA-compliant UW-Madison DoIT server. Access to this data will be limited by granting individuals access via their UW user log-in. Paper study data, such as surveys and contact information, will be entered into a REDCap system managed by ICTR.

Any data stored on a participant's device are stored in an encrypted file and only accessible by that participant, i.e. participants won't have any other participant data on their phone. These data are only collected after the participant has signed into their account and are removed when the participant signs out of the A-CHESS-C or FamCHESS-C application. Any data transferred to and from CHESS servers are done through an encrypted connection.

A list of subject code numbers will be maintained by the UW study coordinator and stored in an electronic spreadsheet. This data will be kept in a secure, limited access,

password-protected file on CHESS servers which are located in the department of Systems and Industrial Engineering in the Mechanical Engineering building on the 4th floor.

The study coordinator will be the only person with access to both the coded study data and the subject identifiers.

When all study activities are complete identifiable information will be destroyed. Deidentified study data will be stored on the secure CHESS servers for potential future unspecified research for which new IRB submissions will be initiated.

Potential Risks:

Regarding risk of misinterpretation of information: Information and resources on the A-CHESS-C/FamCHESS-C apps will be screened by experts from our project team as well as from our Steering Committee for accuracy. Additionally, messages exchanged within the apps will be monitored to make sure the information is accurate and that study participants are using the system for its intended purpose. Inaccurate or harmful statements will be addressed by the CHESS moderator.

Possible breach of confidentiality: All subjects will be assigned a blind code number that will be kept in a locked file in the CHESS office. Data collected from clinic records and smartphone use files will have the name removed and the code number attached by the study coordinator.

Possible break of confidentiality in surveys: Surveys will be conducted by UW staff trained in protecting patient confidentiality. Project staff who have access to the data will not have access to subject names.

Possible risk of being randomized to a less effective treatment group: If it is found that one treatment arm is more effective than an other treatment arm, there is a potential for less effective results for those randomized to the less effective arm. Potential study subjects are notified of this during the consent process.

Possible breach of confidentiality in smartphone use: There is a risk that information provided on the A-CHESS-C/FamCHESS-C apps will be used to the detriment of the subjects. Particular sources of risk include messages written within the discussion groups or personal profiles. Patients will select code names and passwords to use on the apps. They will be instructed to not use their real name as a code name and will be warned of the potential dangers of divulging confidential information (e.g. real names or telephone numbers). Divulging real names could lead to a loss of anonymity and un-wanted contact from study participants outside of the app. The smartphone will automatically collect data on how often and for how long a subject uses each of the A-CHESS-C or FamCHESS-C services.

A-CHESS-C/FamCHESS-C data will be collected by subjects' codename only and will not be attached to real names or identities. Patients will also be asked to set up a pass code on the phone to protect their information in the event someone else finds the phone.

Possible psychological stress regarding sensitive issues: Reporting on sensitive

issues (such as drug and alcohol use and mental health) while using the FamCHESS-C recovery support program may cause anxiety, distress, embarrassment, or feelings of sadness.

Possible risk of economic burden: If a participant uses their own smartphone during the study, CHESS will pay the participant \$50 per month to put toward the cost of their personal cellular plan. Depending on the cost of the participants' cellular plan, the \$50 may not cover the entire monthly charge. The participant would be responsible for paying any amount over **\$50.** Participants are made aware of this during the informed consent process.

For the potential psychological stress regarding sensitive issues: Participants do not have to answer any questions that make them uncomfortable. In addition, study participants can change their minds and choose not to participate at any time.

Findings of Depression/Self-harm/Harm to Others: If a patient subject is determined to be in danger of self-harm, suicide or harm to others when on the phone with a participant during a survey or by reviewing a discussion group post on the smartphone, a crisis intervention plan will be implemented. The UW researchers will contact appropriate others to intervene (e.g., the subject's health care team, and/or their emergency contact).

If potential harm to others is identified, then it may be necessary for us to contact local authorities to ensure your protection or the protection of others. In addition, as researchers, we may be required to report or voluntarily report child abuse to the authorities if the issue arises during the course of this research. Some states have laws requiring or permitting reporting of substance abuse during pregnancy, and if those laws apply, we may be required to report or voluntarily report such information to the appropriate authorities. It is also possible that other users of the app may report substance abuse during pregnancy or other information shared in the app. Participants in this study are not required or expected to share information about pregnancy status in ACHESS-C or FamCHESS-C.Discussion group posts are monitored by study staff daily. If a participant posts a message on A-CHESS-C/FamCHESS-C, we send a message through the app and will try to call the participant. We will ask them if they feel like they are in danger. And provide them a set of resources in their local community.

Mental health referrals will be made when symptoms of major depression, acute anxiety, etc. are indicated in discussion group messages or in the daily or weekly A-CHESS-C/FamCHESS-C survey. If evidence arises that a participant is contemplating suicide, a 4-step protocol will be initiated that includes the following steps: (1) a CHESS staff person will break the code to make identification and emergency intervention possible (e.g., by calling the subject and appropriate authorities); (2) initiate crisis intervention to disengage the writer from a suicide method, engage in stabilizing techniques, and connect the subject with appropriate support; (3) document and followup as appropriate.

If there is evidence of abuse or of a smartphone user being engaged in criminal activity (e.g., a discussion group being used to sell an illegal drug), we may need to inform an

appropriate authority. Hence our consent form will include the following statement: "I understand that subject anonymity and data confidentiality cannot be maintained if A-CHESS-C or FamCHESS-C finds evidence of abuse, suicidality, or criminal activity."

If participants are incarcerated, no research activities would occur during the time of incarceration. Participants can contact the UW study coordinator if they are released during the original study period and would like to continue on study.

The researchers may also take participants out of the study, even if they want to continue, if they use the phone in an inappropriate manner (i.e. messages including nudity, threats, racism, bigotry), research staff will delete the inappropriate messages and follow up with the participant. If the behavior continues, research staff may decide to withdraw the participant from the study without their consent for their best interest as well as others on the study

If participants experience any crises during the study period, they will be instructed to contact their clinician if currently in treatment. If participants have crises after hours, they will be instructed to call 911 for imminent risk or go to a local emergency room crisis center. All participants will be provided with a listing of crisis hotline numbers and community resources that participants may access 24/7, such as the National Drug Abuse [contact]), the National Domestic Violence [contact]), or a Crisis Hotline for any crisis [contact]).

Lost or Stolen Smartphone: Participants will be informed that if the phone is in the hands of another person there is the potential that someone might see the information they stored on the phone (personal contacts, text messages). Participants are advised to make their phone password protected to reduce the risk of someone being able to see their information if the phone is lost or stolen.

Phone service for the study phone is terminated at the end of the 8-month intervention period. Participants may feel some loss when they no longer have that service. The study coordinator will explain this prior to informed consent and will inform the participants well in advance of the service ending so they have time to get their own service if they wish.

If study phones are lost or stolen they will not be replaced.

To help us further protect participant privacy, we will obtain a Certificate of Confidentiality from the National Institutes of Health.

Potential Benefits

A potential benefit may be a reduction in heavy drinking days for your family partner and improvement in quality of life for you and your family partner.

Although taking part in this research may not benefit you directly, it may benefit other people in the future by helping us learn more about how a smartphone with a recovery support system can improve patient and family partner quality of life and improve the

health care given to others with substance abuse problems.

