6.0 MEASUREMENT OF EFFECT

Variables reflect the conceptual model (see Figure 3, above) and study aims. Measures chosen have good psychometric properties with similar populations. Where possible, we used PhenX and PROMIS measures (e.g. PROMIS 29.2) so that results are comparable to other studies.⁸⁵ Our primary outcome is percent days of heavy drinking, but given 2015 FDA draft guidelines we also include number of patients with *no* heavy drinking days per period as a secondary outcome.⁸⁶ Table 2 lists our measures, number of questions, and sources, with references to validation studies where relevant. In the R34, we collected much of the same data we propose to collect in the RCT. Survey completion time averaged about 90 minutes.

Table 2: Proposed Measures, Scales, and Sources for Study Outcomes and Other	
Variables	

MEASURE	WHO	SOURCE	REFERENCE	# QUEST	TIME (MONTH)
		Primary Outcomes			
% days heavy drinking	Drinker	Timeline Follow Back ⁸⁷	Johnston et al. ⁸⁸	7	0, 4 , 8, 12
Quality of life	Dyad	PROMIS 29.2	Hamilton et al.85	29	0, 4, 8, 12
		Secondary Outcomes			
Relationship satisfaction	Dyad	OQ-45.2 ⁸⁹	Beckstead et al.89	45	0, 4 , 8, 12
Physical/psychological conflict	Dyad	Rev. Conflict Tactics	Straus et al.90	20	0, 4 , 8, 12
No heavy drinking days	Drinker	Timeline Follow Back ⁸⁷	Johnston et al. ⁸⁸	7	0, 4 , 8, 12
% days alcohol or drug use	Drinker	Timeline Follow Back ⁸⁷	Johnston et al. ⁸⁸	7	12
COVID vaccination completion	Dyad			1	0, 4 , 8, 12
Drinking/drug problems	Drinker	Clinical evaluation guide	Spitzer et al.91	5	0, 4 , 8, 12
	Ē	Exploratory outcomes			
Crisis healthcare use (ER, 30 day readmits)	Dyad	Treatment Services Reviews	McCollister & French ⁹²	3	0, 4 , 8, 12
% days alcohol or drug use	Partner	TLFB last 60 day	Collins et al. ⁸⁷	11	0, 4 , 8, 12
Satisfaction with technology	Dyad	Tech Accept Model93	Szajna ⁹⁴	26	4, 8, 12
		Mediators			
Competence	Dyad	CCQ / # of skills used	Schroder & Ollis ⁹⁵	11	0, 4 , 8, 12
Relatedness	Dyad	Revised Important People	Zwiak et al.96	14	0, 4 , 8, 12
Motivation	Dyad	Brief Self Control Scale	Tangney et al.97	13	0, 4 , 8, 12
Reductions over 8 months % days alcohol or drug use	Drinker	Timeline Follow Back ⁸⁷	Johnston et al. ⁸⁸	7	0, 4 , 8
For ACHESS-C vs. FamCHESS-C: use of app	Dyad	Smartphone data	N/A	0	0, 4 , 8, 12
		Moderators			
Sex	Drinker			1	0
Concurrent treatment services	Drinker	TSR	McLellan et al.98	10	0, 4 , 8, 12
Severity baseline alcohol	Drinker	Smartphone data	N/A	0	0, 4 , 8, 12

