8.0 STATISTICAL CONSIDERATIONS

Data Analysis Plan. The analysis will: 1) explore differences among the three arms over the 8-month active intervention phase and then the 4-month follow-up phase of the RCT; 2) explore the conceptual model (see Figure 3) that considers the relations between the primary and secondary outcomes, and drinker and partner mediators, moderators, and covariates; and 3) examine how the dyad's demographic characteristics (e.g. young drinker and older partner) affect intensity and length of ACHESS-C and FamCHESS-C use and SDT mediators of relatedness, motivation, and competence on study outcomes.

Assumptions and randomization effect. We will report descriptive statistics for all demographic and clinical variables in both arms to ensure that randomization produced comparable groups; if not, variables with significant differences will be included as covariates in a sensitivity analysis. Sensitivity analyses (with and without covariate adjustment) will determine the robustness of covariate-related error control. All outcome variables will be examined using standard summary statistics, visualizations, and tests for normality and homoscedasticity. Data will be transformed for continuous outcomes that do not meet the assumptions of a normally distributed outcome.

Effects of study arm on primary and secondary outcomes (Aim 2). Linear mixed effects models (LMEM)—which account for dependence among successive observations on the same drinker and can address incomplete data—will be used to examine effects of study arm (FamCHESS-C vs. ACHESS-C vs. control, a between-subjects factor) on drinker outcomes over time. We will conduct specific treatment X time contrasts both between and within groups to test time-based effects. For binary, count, and other non-normal data, generalized linear mixed effects models will be used.

Mediation of effects of study arm on primary outcomes (Aim 3). Structural equation modeling (SEM) will explore the effects of mediation on the relation between study arms and our two primary outcomes. We anticipate that the impact of study arm on drinker heavy drinking days and dyad quality of life will be mediated by SDT (competence, relatedness, and motivation) and by drinker's interim change in percent alcohol and drug use days. SEMs involving app use will be run separately for only the ACHESS-C and FamCHESS-C arms.

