Moderation of study arm on primary outcome (Aim 3). We will test whether the four variables listed in Figure 3 moderate the effects of the intervention on outcomes. The moderators will be entered as interaction terms in the models described above for the primary outcomes, testing each moderator separately. We will conduct exploratory analyses on whether these moderation effects are also observed for secondary outcomes.

Power. Our primary outcome used to power the study is reduction in percent of heavy drinking days. In our prior study of ACHESS with drinkers coming out of inpatient treatment for AUD, we found an effect size of ACHESS vs. usual care of d=.31 for this outcome.¹⁰⁰ Since then, ACHESS has been improved, and in the proposed study we will incorporate COVID-related content to help drinkers cope with pandemic stresses. Given this, we expect an effect size of d=.40 for the comparison of smartphone control vs. ACHESS-C.

We powered the analysis to be able to detect an effect size of d=.40 for smartphone control vs. ACHESS-C, and then the same magnitude of effect for ACHESS-C vs. FamCHESS-C. It is reasonable to expect an effect of roughly d=.80 for FamCHESS-C vs. smartphone control, given the strong effects observed in an RCT of ABCT, where the effect size for reductions in percent risky drinking days was d=.79.¹⁰¹

We ran the power analyses two ways, based on two different estimates of likely attrition. In prior ABCT and ACHESS studies, 10–21% attrition at 9 and 8 months, respectively, was observed. ¹⁰¹ As the analyses below indicate, an initial sample of 198 dyads would give us adequate power at either rate of attrition.

Starting with a sample of 198, 10% attrition would mean a sample size at 8 months of 180. Across 10,000 LMEM simulations, with post-attrition N=180, we would have power >90% to detect the study arm X time interaction. Starting with a sample of 198, 21% attrition would mean a sample size at 8 months of 159. Across 10,000 LMEM simulations, with post-attrition N=159, we would have power >85% to detect the study arm X time interaction. We will recruit 198 dyads.

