Qualitative Analyses (Aim 4). Transcripts of qualitative interviews concerning perceived difficulties and benefits of app use will be examined using Braun and Clarke's¹⁰² six-phase procedure for thematic analysis: 1) familiarization with data, 2) generation of initial codes, 3) identifying instances of themes, 4) review of themes, 5) defining and naming themes, 6) production of findings. To improve consistency and accuracy, coders will work separately using NVivo software; findings will be compared and discussed until consensus is reached.

Interim Analyses and Stopping Plan. The interim analyses are solely to check whether the stopping plan needs to be implemented. They will not be reported as tests of our hypotheses and thus will not inflate Type 1 error. We will engage in the following practices: 1) We will report any fatalities as they occur, as required by the university IRB. 2) Our statistician will conduct interim analyses at months 18 and 27 after the start of the study (9 and 18 months after recruiting begins), examining our primary outcome of substance use days in the two arms. She will share the results with UW's independent Data Safety and Monitoring Board but not with the Pls unless instructed to do so by the Board. Because all of our prior research has been designated low-risk by

the IRB, we anticipate the same designation in this case. Barring exceptional disparities in outcomes between conditions, we do not anticipate stopping the trial. As an *a priori* rule, we believe we should stop if our primary outcome of functional health shows a T-score difference greater than 6 (averaged across components of the PROMIS-29). A T-score of 6 is at the very upper end of the clinically meaningful differences for PROMIS-29 components (e.g. physical function, pain, fatigue).^{22,30} We have no reason to anticipate such an occurrence. We will follow Data Safety Monitoring Board guidance on this matter.

Missing Data. In previous RCTs, we completed about 85% of interviews through 12 months and kept missing data on core interview items to about 2%. We expect these rates in this study. We will identify missing data patterns and use pattern-mixture modeling to test the sensitivity of our analysis to missing data assumptions.¹⁰³⁻¹⁰⁶ We will conduct other sensitivity analyses after imputing missing data with a range of plausible values based on assumptions for the missing data (e.g. best-case, worst-case; with and without multiple imputation).¹⁰⁷⁻¹⁰⁹

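### Two primary outcomes and three hypothesised arm contrasts have no stated significance level, testing order or multiplicity rule, and the primary-outcome labels conflict

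*Combined protocol and SAP*

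**What the plan says.** Section 5.0 (Aim 2, study design and outcomes) gives "Primary outcomes: 1) drinker % heavy drinking days, 2) dyad quality of life", matching Aim 2 in Section 2.0. In Section 8.0, the mediation paragraph refers to "the relation between study arms and our two primary outcomes". Hypothesis 1 reads "Outcomes will be more favorable in FamCHESS-C relative to ACHESS-C, and both will be more favorable relative to smartphone control", which is three pairwise orderings.

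The Aim 2 analysis in Section 8.0 is a mixed model with arm as a three-level factor, followed by this sentence: "We will conduct specific treatment X time contrasts both between and within groups to test time-based effects". The contrasts are not listed or ranked. No significance level or sidedness appears anywhere in the document. The only remark on Type 1 error concerns the interim looks: "They will not be reported as tests of our hypotheses and thus will not inflate Type 1 error".

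Other places label the primary outcome differently. Section 6.0 says "Our primary outcome is percent days of heavy drinking", in the singular. The power paragraph says "Our primary outcome used to power the study is reduction in percent of heavy drinking days". The interim plan speaks of "examining our primary outcome of substance use days in the two arms", although percent days of alcohol or drug use is a secondary outcome in Sections 2.0 and 5.0.

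**The concern.** If each contrast on each primary outcome can support a claim, the plan has six chances of a positive primary result and no rule that limits the overall error. Nothing written says which result decides the trial or at which visit. Because the labels conflict, the choice of headline outcome could also be made, or appear to have been made, after the data are seen. A reader of the final report could not tell a planned confirmatory finding from the best of several.

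**Working it through.** **Inputs from the documents.** There are two primary outcomes and three orderings (Section 5.0). The sample is 198 dyads, 66 per arm, with about 180 expected at 8 months, so 60 per arm (Sections 5.0 and 7.0). The planned effects are d = 0.40 for each adjacent pair and about 0.80 for FamCHESS-C versus control (Section 8.0).

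**Assumptions.** Two-sided 5% per test, since none is stated; correlation between the two outcomes of 0 to 0.5; approximately normal estimates.

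**1. The plan's own power figure.** The plan gives power above 90% at N = 180 and above 85% at N = 159 for the arm-by-time interaction. With arm means 0, 0.4 and 0.8, f² = (0.4² + 0 + 0.4²)/3 = 0.107. The noncentrality is N × f² = 19.2 at N = 180 and 17.0 at N = 159. A 2-df F test at 5% then has power 98% and 96%, which is compatible with the stated lower bounds. The exact simulation cannot be reproduced, because the significance level, variances and repeated-measures correlation are not given. A single d = 0.40 contrast at 60 per arm has standard error √(2/60) = 0.183, a ratio of 0.40/0.183 = 2.19, and power of about 59% (54% at 53 per arm). A single contrast would exceed the stated bounds only with a repeated-measures correlation of about 0.8. The stated power therefore fits the overall test more readily than any one contrast.

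**2. Number of tests.** 3 contrasts × 2 outcomes = 6. If they were independent, the error would be 1 − 0.95⁶ = 26.5%. The three contrasts share arms, so this overstates it, and simulation is needed.

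**3. Error with no arm differences** (simulated, 2,000,000 draws per setting):

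| Reading | Correlation 0 | 0.3 | 0.5 |
|---|---|---|---|
| One outcome, three contrasts standing alone | 12.2% | 12.2% | 12.2% |
| Two outcomes, six contrasts standing alone | 22.9% | 22.4% | 21.3% |
| Two outcomes, contrasts read only after a significant overall test | 9.8% | 9.6% | 9.1% |
| Six standing alone, favourable direction only | 12.7% | 12.3% | 11.7% |

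One outcome with the overall test first gives 5.0%. With three arms this is a closed test: any two true pairwise nulls imply that all three arms are equal, and the overall test covers that case.

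**4. Power cost of testing the overall effect first** (simple comparison at 60 per arm, 5%):

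| True means (control, ACHESS-C, FamCHESS-C) | Contrast | Standing alone | After overall test |
|---|---|---|---|
| 0, 0.4, 0.8 (planned) | Adjacent pairs | 58-59% | 58-59% |
| 0, 0.4, 0.8 (planned) | FamCHESS-C vs control | 99% | 98% |
| 0, 0.4, 0.4 | Either app vs control | 58-59% | 51% |
| 0, 0.2, 0.4 | FamCHESS-C vs control | 58% | 45% |

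At 2.5%, the first Holm step, an adjacent contrast under the planned effects has about 47-48% power and the overall test 96%.

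**The case against.** The best defence is that the plan can be read more strictly. Arm enters as a single three-level factor and only the overall interaction is powered, so the contrasts may be meant as follow-up to that test. On that reading the rate is 9-10%. This stands as a possible reading, but it is not written down, and 9-10% is still above 5%.

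Several stronger conclusions are tempting, and the documents do not support them:

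- **That the error rate is 21-23%.** No significance level is stated, and the figure requires six stand-alone tests. It is the upper of two open readings.
- **That there is a one in five chance of a false claim of benefit.** Hypothesis 1 is directional, and the 21-23% includes results favouring control. Favourable-direction errors are about 12% when the contrasts stand alone.
- **That no lead outcome exists.** Section 6.0 and the power paragraph both favour percent heavy drinking days. The fault is conflicting labels.
- **That the stopping rule's functional health is yet another primary outcome.** It is measured by PROMIS-29, the instrument Table 2 lists for quality of life, so it is plausibly the second primary outcome under another name.
- **That testing every visit, or change within arms, inflates the primary error further.** No text makes each visit a separate primary test; Sections 5.0 and 7.0 point to an 8-month analysis. Within-arm contrasts are planned but are not tests of Hypothesis 1, and the documents give no figures for change in the control arm.

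The substance-use-days label is a genuine mismatch. It sits in an interim plan that is not used to test the hypotheses, so it adds no final test.

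**Conclusion.** The concern holds as a missing testing rule combined with inconsistent primary-outcome labels. The false-positive rate over the primary contrasts is about 9-10% or 21-23%, depending on a rule the plan does not state. Both ranges rest on an assumed two-sided 5%, no true arm differences and a between-outcome correlation of 0 to 0.5; at 0.8 the rates fall to about 8% and 18%. If percent heavy drinking days alone leads, the rates are 5% with the overall test first and 12% without. The design and sample need not change, but the rule should be fixed before outcome data are compared by arm.

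**What to change.** In Section 8.0:

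1. State two-sided 5%.
2. For each primary outcome, make the decisive test the 2-df comparison of the three arms on change from baseline to month 8, taken from the planned mixed model. Interpret the three pairwise contrasts, at the same level, only if it is significant. Specify the 2-df form: an interaction pooled over all follow-up visits is a different hypothesis and would not give a closed test of the month-8 contrasts.
3. Apply Holm across the two primary outcomes, starting at 2.5%, or name percent heavy drinking days as the single lead outcome. If Holm is used, say when the other outcome moves to 5%. For control to extend to the pairwise contrasts, this should happen only once the overall test and all three contrasts on one outcome are significant at 2.5%. Releasing it on the overall test alone could leave 2.5% + 5% = 7.5% at risk when one contrast on the first outcome is truly null.
4. Report months 4 and 12 and within-arm changes as supportive estimates with confidence intervals.
5. Reconcile the primary-outcome wording in Section 6.0 and the interim plan with Section 5.0.

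**Cost.** If both outcomes stay primary, this is text in Sections 6.0 and 8.0, plus the power cost shown above. The first-step Holm figure is the less favourable case, since the second outcome may be tested at 5%. Naming one lead outcome avoids the split, but it demotes quality of life and changes Sections 2.0 and 5.0 as well. That choice is the sponsor's.
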